# Part 2 (Efficacy) - Overview

All participating countries and centers will be eligible for Part 2 (Efficacy).

Part 2 is a double-blind, randomized treatment epoch. Patients will receive either LCZ696 or enalapril, and matching placebo for enalapril or LCZ696, respectively. The target dose of LCZ696 for Groups 1 and 2 is dose level 4 and for Group 3 is dose level 4x, and was selected based on the Part 1 PK/PD results. Blinded study drug will be titrated to the target dose as tolerated per the safety monitoring criteria (Table 3-3) (e.g. if the patient does not experience adverse events that include symptomatic hypotension, worsening renal function, or hyperkalemia). AEs or conditions that preclude initiation or up-titration of study drug can include abnormalities in laboratory chemistry values based on local laboratory normal reference ranges and the Investigator's judgment. Additional safety monitoring will be required for Group 3 patients. Starting with the first dose of study medication, vital signs must be checked for up to 4 hours after the initial dose at each dose level (i.e. dose levels 1x through 4x, as applicable). Note: this does not apply for up-titrations following study drug interruptions or down-titrations up to the prior achieved maximal dose level). See Appendix 13 for details.

Table 3-3 Safety monitoring criteria for initiation/up-titration of study drug

	 
Parameter	Description
Potassium level	K ≤ 5.4 mmol/L (mEq/L)
Kidney function	eGFR (calculated using the modified Schwartz formula) ≥ 30% mean GFR for age (Appendix 10, Table 22-1)
Kidney function  Blood pressure	eGFR reduction < 35% compared to randomization Visit 401 (Part 2). SBP > than the calculated 5th percentile SBP for
AEs or conditions	age as described in Appendix 4  No conditions that preclude continuation
	according to Investigator's judgment, including hypotension.

## Part 2 (Efficacy) - Pre-randomization/screening epoch, Visit 301

All patients will be consented for Part 2 efficacy (parent/legal guardian ICF and if applicable, patient assent) before any study-specific procedures are performed. All patients entering Part 2 must fulfill all inclusion criteria and none of the exclusion criteria at Visit 301 (Part 2 Efficacy-Pre-Randomization/Screening). Local laboratory evaluations are required to assess the patient's eligibility at Visit 301 (refer to Table 6-1, Table 6-2 and Section 6.5.4).

Patients may enter Part 2 (Efficacy) via two pathways:

- Patients participating in Part 1 will be re-evaluated to assess all inclusion and exclusion criteria. A repeat assessment of LVEF or fractional shortening is only required if the last assessment of LVEF or fractional shortening was > 1 month prior to Visit 301
- Patients that did not participate in Part 1 (PK/PD) will be evaluated to assess all inclusion and exclusion criteria for participation in Part 2 (Efficacy).

The screening period will be up to three weeks. No study medication will be administered during this time.

Amended Clinical Trial Protocol Version 07 (Clean)

Qualifying LVEF or fractional shortening measurements will be based on a locally obtained echocardiogram, MRI, MUGA, or left ventriculogram. If these qualifying measurements are not available within 1 month of Visit 301 (Part 2 Efficacy- Pre-Randomization/Screening), then an echocardiogram should be obtained during the screening period.

Part 2 screening laboratory assessments should be performed locally. Only patients with the required values per the entry criteria will be eligible to continue in the study.

Both hospitalized patients and outpatients are eligible for participation in Part 2 (Efficacy). A hospitalized patient is defined as a patient who is being treated in the hospital at the time of Visit 401 (Part 2 Efficacy - Randomization). An outpatient is a patient who is screened in stable health status and can initiate study medication intake in an ambulatory setting.

# Part 2 (Efficacy) - Randomized treatment epoch (Visit 401 to Visit 416/499)

The Part 2 randomized treatment epoch begins at Visit 401. Part 2 will enroll 360 patients. Patients are required to discontinue their enalapril or other ACEI at least 36 hours before taking blinded study drug at randomization to minimize the potential risk of angioedema due to overlapping ACEI-NEP inhibition. Patients taking an ARB or renin inhibitor are required to discontinue their ARB or renin inhibitor on the day of randomization (i.e. patient should not have taken ARBs, or renin inhibitor on the day of randomization).

At randomization (Visit 401), patients who meet eligibility and safety criteria will be randomized to 1 of 2 treatment arms: double-blind enalapril bid or LCZ696 bid. The initial study drug dose started at randomization for Group 1 and 2 is dose level 1 or 2 (Table 3-5), and for Group 3 is dose level 1x or 2x (Table 3-6). Patients who are ACEI/ARB naïve or on low dose ACEI/ARB (dose levels 1 or 2; Table 3-4) prior to randomization should start at dose level 1 or 1x at randomization, depending upon the age group (Table 3-5, Table 3-6). Patients who are on higher doses of ACEI/ARB (dose levels 3 or 4; Table 3-4) prior to randomization may start at dose level 2 or 2x, based on age group (Table 3-5, Table 3-6). Given the patient's condition is often dynamic, patients may start, depending upon the age group, on dose levels 1 or 1x or 2 or 2x at randomization based on Investigator judgement.

Patients will continue taking their background HF therapy except for ACEIs and/or ARBs, which are replaced by the study medication. The concomitant use of ACEIs, ARBs, or renin inhibitors with study medication is strictly prohibited.

Table 3-4 Part 2 (Efficacy): Total daily dose levels of commonly prescribed ACEI/ARBs to guide selection of the study medication starting dose

Dose levels for pediatric formulation	Enalapril/Lisinopril total daily dose	Captopril total daily dose	
Dose level 1	0.1 mg/kg	0.3 mg/kg	
Dose level 2	0.2 mg/kg	0.6 mg/kg	
Dose level 3	0.3 mg/kg	1.2 mg/kg	
Dose level 4	0.4 mg/kg	1.5 mg/kg	
Dose levels for adult formulation	Enalapril/Lisinopril total daily dose	Captopril total daily dose	Cilazapril total daily dose
Dose level 1	5 mg	18.75 mg	0.5 mg

Dose level 2	10 mg	37.5 mg	1.0 mg
Dose level 3	15 mg	75 mg	2.5 mg
Dose level 4	20 mg	150 mg	5.0 mg
Dose levels for pediatric formulation	Valsartan total daily dose	Losartan total daily dose	Candesartan total daily dose
Dose level 1	0.7 mg/kg	0.4 mg/kg	0.2 mg/kg
Dose level 2	1.4 mg/kg	0.7 mg/kg	0.25 mg/kg
Dose level 3	2.0 mg/kg	1.0 mg/kg	0.32 mg/kg
Dose level 4	2.7 mg/kg	1.4 mg/kg	0.64 mg/kg
Dose levels for adult formulation	Valsartan total daily dose	Losartan total daily dose	Candesartan total daily dose
Dose level 1	40 mg	25 mg	4 mg
Dose level 2	80 mg	50 mg	8 mg
Dose level 3	160 mg	75 mg	16 mg
Dose level 4	320 mg	100 mg	32 mg

For age groups 1 and 2, the target dose for enalapril is 0.2 mg/kg bid (0.4 mg/kg total daily dose) with a maximum dose of 10 mg bid (20 mg total daily dose). For age groups 1 and 2, the target dose for LCZ696 is projected to be 3.1 mg/kg bid. Based on the PK/PD results from Part 1 for Group 3 patients, the target dose for LCZ696 (dose level 4x) will be 2.3 mg/kg bid. In addition, for Group 3 patients who turn 1 year old during the study, consideration should be given to uptitrate to a dose of 3.1 mg/kg bid (dose level 5x). See Appendix 14 for details. The LCZ696 dose is not to exceed 200 mg bid irrespective of the body weight (Table 3-5, Table 3-6). The actual target dose (dose level 4 or 4x, depending upon age group) and lower dose levels (1, 2, 3 or 1x, 2x, 3x, depending upon age group) of LCZ696 for Part 2 were determined based on PK and PD results from Part 1 of the study.

Study drug is titrated to target dose level 4 for Group 1 and 2, or to target dose level 4x for Group 3, as tolerated based on the safety monitoring criteria approximately every 2 weeks beginning at Visit 401 (Part 2 Efficacy – Randomization) and continuing at Visits 402 and 403 (Table 3-3). Investigators have the option to schedule a patient for an additional visit (Visit 404; 6 weeks post-randomization) in order to complete the titration to the target dose. Additional safety monitoring will be required for Group 3 patients. Starting with the first dose of study medication, vital signs must be checked for up to 4 hours after the initial dose at each dose level (i.e. dose levels 1x through 4x, as applicable). Note: this does not apply for up-titrations following study drug interruptions or down-titrations up to the prior achieved maximal dose level) See Appendix 13 for details. Unscheduled visits may be necessary to assess the patient and/or adjust study medication as needed. Group 3 patients who turn 1 year old during the study and for whom study drug is to be up-titrated based on the safety monitoring criteria, a scheduled or unscheduled visit may be used for these up-titration visits. See Appendix 14 for details.

Single PK samples will be collected during Part 2 (Efficacy) at the following visits: Visit 403, Visit 406, and Visit 416/499 (Week 52/End of Study) (see Appendix 15 for USM exception). Additional samples for PK may be considered if patient has an unscheduled visit.

In approximately 24 Group 2 patients, sparse PK blood samples will be collected at steady-state at 3 time-points on the same day, at Visit 405 or at a subsequent scheduled or unscheduled visit

(except visits 406 and 416/499), when the patient is on Dose-Level 4 or at his/her highest tolerated dose for at least 1 week. Refer to Section 6.6.2 for additional PK information.

To assess the patient's eligibility to titrate to the next dose level, local laboratories should be used.

Table 3-5 Part 2 (Efficacy): Study drug dose levels for double-blind enalapril and LCZ696 for age groups 1 and 2

Dose levels for pediatric formulation	Enalapril dose	LCZ696 dose †	
Dose level 1	0.05 mg/kg bid.	0.8 mg/kg bid.	
Dose level 2	0.1 mg/kg bid.	1.6 mg/kg bid.	
Dose level 3	0.15 mg/kg bid.	2.3 mg/kg bid.	
Dose level 4	0.2 mg/kg bid.	3.1 mg/kg bid.	
Dose levels for adult formulation	Enalapril dose	LCZ696 dose †	
Dose level 1	2.5 mg bid.	50 mg bid.	
Dose level 2	5 mg bid.	100 mg bid.	
Dose level 3	7.5 mg bid.	150 mg bid.	
Dose level 4	10 mg bid.	200 mg bid.	

†Note: LCZ696 target dose (dose level 4) and other dose levels shown in table are based on target dose of LCZ696 3.1 mg/kg bid. LCZ696 target dose has been verified by Part 1 PK/PD.

Table 3-6 Part 2(Efficacy): Study drug dose levels for double-blind enalapril and LCZ696 for age group 3

Dose levels for pediatric formulation	Enalapril dose	LCZ696 dose †	
Dose level 1x	0.05 mg/kg bid.	0.8 mg/kg bid.	
Dose level 2x	0.075 mg/kg bid.	1.2 mg/kg bid.	
Dose level 3x	0.1 mg/kg bid.	1.6 mg/kg bid.	
Dose level 4x	0.15 mg/kg bid.	2.3 mg/kg bid.	

†Note: LCZ696 target dose 2.3 mg/kg (dose level 4x) is based on Part 1 PK/PD Safety data. The other dose levels for LCZ696 shown in table are based on target dose of LCZ696 2.3 mg/kg bid and Part 1 PK/PD Safety data. For Group 3 patients who turn 1 year old during the study, consideration should be given to up-titrate to a dose of 3.1 mg/kg bid (Dose Level 5x). See Appendix 14 for details.

Randomized, ongoing, Part 2 Age Group 3 patients (i.e. patients who are 1 month to <1 year old at randomization) who are safely tolerating Dose Level 4x (i.e. LCZ696/Placebo, 2.3 mg/kg bid / Enalapril/Placebo 0.15 mg/kg bid) for at least 2 weeks, and who turn 1 year old during the study, may be up-titrated to Dose Level 5x (LCZ696/Placebo, 3.1 mg/kg bid / Enalapril/Placebo 0.2 mg/kg bid), if it is the patient's best interest to be up-titrated based on the medical judgement of the investigator. See Appendix 14, Table 26-1 for Dose Level 5x up-titration information for Age Group 3 patients.

Study drug dose level adjustments should be based on overall safety and tolerability. Patients should be titrated to the next dose level if there is no symptomatic hypotension, hyperkalemia, worsening renal function, or other AEs per the Investigator's judgment as shown in Table 3-3.

Additional safety monitoring will be required for Group 3 patients with each initial dose level up-titration. See Appendix 13 for details.

Every attempt should be made to achieve and maintain patients on the target study drug dose level throughout Part 2 (Efficacy). If, in the opinion of the Investigator, the patient does not tolerate the assigned study medication, the Investigator should consider whether non-diseasemodifying medication (e.g. calcium channel blockers, diuretics, α-blockers) can be reduced to rectify the situation. The Investigator may adjust doses of disease-modifying medications (e.g. beta-blockers, aldosterone antagonists) if it is believed that they are the most likely cause of the adverse effect. If adjustment/elimination of concomitant medications is not possible or does not alleviate the side effects of concern, the Investigator may down-titrate or interrupt the study drug. Refer to Section 5.5.5 for guidance on permitted study drug dose adjustments and interruptions. If the reason for a dose adjustment is due to an adverse event, an adverse event should be reported.

At each visit after randomization (Part 2 Efficacy - Visit 401), the patient's medication compliance, safety, and tolerability of the study medication are assessed. This will include, but not be limited to signs and symptoms of hypotension, serum potassium level, and renal function. Patients who experience angioedema as determined by the Investigator at any time during the double-blind epoch must be discontinued from the study.

Both scheduled and unscheduled visits can be utilized for up-titration/down-titration throughout the study based on Investigator judgment (Section 5.5.5) for re-evaluation of safety criteria parameters and study drug management.

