#### Permitted dose adjustments and interruptions of study treatment 5.5.5

The study drug is up-titrated every 2 weeks as tolerated to target dose (level 4 for Group 1 and 2, and 4x for Group 3) as outlined in (Table 3-5 and Table 3-6) based on the safety monitoring criteria (Table 3-3). Additional safety monitoring will be required for Age Group 3 patients with each initial dose level up-titration. See Appendix 13 for details. Following up-titration, the maximum tolerated or target dose will then be maintained for the duration of the study. Both scheduled and unscheduled visits can be utilized for up-titration/down-titration throughout the study based on Investigator judgment.

For patients who are unable to tolerate the protocol-specified dosing scheme, dose level adjustments and interruptions of study treatment are permitted in order to keep the patient on study drug. The following guidelines should be followed:

- The Investigator should adjust doses of concomitant medications if it is believed that they are the most likely cause of an adverse effect
- If adjustment/elimination of concomitant medications is not possible or does not alleviate the side effects of concern, the Investigator may down titrate to the next lower study drug dose level down (Table 3-5 and Table 3-6) to temporary or permanent discontinuation of study drug
- The patient should be rechallenged with the higher dose when the Investigator feels it is appropriate to do so per the directions provided below in this section
- If the study drug is temporarily or permanently discontinued, then the patient should continue to attend the study visits and be followed until the completion of the study

Patients may be seen at any time for unscheduled visits during the randomized treatment epoch for reevaluation of safety criteria parameters. Study drug dose level adjustments should mainly be based on overall safety and tolerability with focus on a) hyperkalemia; b) symptomatic hypotension; and c) renal dysfunction. Local laboratory assessments of serum sodium, potassium, creatinine, and eGFR (calculated based on the modified Schwartz formula (Schwartz 2009) will be utilized. Refer to Appendices 15, 16, and 17 for treatment guidelines for renal dysfunction, management of hypotension and hyperkalemia, respectively.

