# Study drug restart after temporary treatment interruption

Patients who have temporarily discontinued study drug should be restarted as soon as possible as deemed appropriate by the Investigator. The Investigator should restart the patient on the study drug at the most appropriate dose level (Table 3-5 and Table 3-6) as per the Investigator's clinical judgment. Patients must discontinue their ACEI medication(s) 36 hours prior to restarting study drug to allow for an ACEI-free washout period. If the patient does not tolerate the newly restarted study drug dose level, s/he may be down titrated again (if appropriate) or the study medication may be temporarily discontinued again.

Patients restarted on the study drug will retain their original randomization and study identification numbers.

Investigators may discontinue the study drug due to serious or intolerable AEs suspected to be causally related to study drug. If study drug is discontinued for any reason, the exact time and date of study drug discontinuation must be recorded on the DAR CRFs. In addition, patients who discontinue study drug should continue to be followed at all study visits as defined in the protocol (Table 6-1 and Table 6-2).

The use of an open-label ACEI, ARB or a renin inhibitor during a period in which the patient may be off study drug is discouraged. However, if a patient off study drug has started openlabel treatment with an ACEI, the ACEI must be discontinued ≥36 hours prior to restarting study drug. Patients who have temporarily discontinued study drug and are presently taking an ARB or a renin inhibitor must discontinue their current ARB or renin inhibitor on the day study drug is started. These changes must be recorded on the DAR and Concomitant Medication CRFs.

If the patient is discovered to be pregnant during the course of the study, the patient should discontinue study drug immediately. Meanwhile, the patient should continue to attend scheduled study visits.

Refer to (Section 6.5.7 and Section 7.7) for further details on pregnancies and reporting guidelines.

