#### 5.6.2 Discontinuation of study treatment

Patients may voluntarily discontinue study treatment for any reason at any time.

The emergence of the following circumstances will require permanent study drug discontinuation:

- Withdrawal of informed consent
- Investigator believes that continuation would be detrimental to the patient's well-being
- Suspected occurrence of angioedema; a patient with any signs or symptoms of clinically significant angioedema should be thoroughly evaluated by the Investigator

The emergence of the following circumstances will require temporary or permanent discontinuation (study drug may be restarted once these circumstances no longer exist):

- Use of an open-label ACEI, ARB or renin inhibitor
- Pregnancy and post-pregnancy during lactation period (Section 7.7)

Study drug may be discontinued at the Investigator's discretion if any of the following occurs:

- Any severe or suspected drug-related AE
- Any other protocol deviation that results in a significant risk to the patient's safety

The appropriate personnel from the site and Novartis will assess whether study drug should be discontinued for any patient whose treatment code has been broken inadvertently for any reason.

If permanent discontinuation of study treatment occurs and the patient/parents/guardians have not withdrawn consent, the patient should NOT be considered withdrawn from the study. The patient should return to the clinic as soon as possible, after discontinuation of study drug, for a study treatment discontinuation visit. Treatment discontinuation visit assessments detailed in the "unscheduled treatment discontinuation visit" (UNS) in Table 6-1 and Table 6-2 should be completed and recorded in the CRF. The Investigator must determine the primary reason for the patient's premature discontinuation of study treatment and record this information on the Dosage Administration CRF.

After study treatment discontinuation, the following minimum data should to be collected at clinic visits or via telephone visits:

new / concomitant treatments

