Patients taking open-label liquid enalapril should obtain study drug from the site monthly until Part 2 begins (due to the 1 month storage life of liquid enalapril). If the patient is taking Epaned liquid enalapril that has a 2 month storage life, patients must obtain open-label enalapril every 2 months until Part 2 begins. If the parent/caregiver comes to the site without the patient to pick up the open label liquid enalapril, a telephone call to the patient ( $\geq 6$  years old) can be used in conjunction with the parent/caregiver visit. At the telephone visits for Part 1, the following assessments will not be performed: vital signs, abbreviated physical exam, weight, abbreviated laboratories and urine pregnancy.

Visit 199 and 299 are end of LCZ696 PK/PD first dose visit and second dose visit, respectively. For the patient that only participates in the LCZ696 PK/PD first dose, the Visit 199 may occur on the same day as Visit 301, if patient is going to participate in Part 2. For the patient that participates in the LCZ696 PK/PD first and second PK doses, Visit 199 may occur on the same day as Visit 201. For the patient that only participates in the LCZ696 PK/PD second dose, Visit 299 may occur on the same day as Visit 301, if patient is going to participate in Part 2. Visit 301 is a pre-randomization screening visit for Part 2.Part 2 of the study consists of Visits 301 to 499. Visit 401 (randomization) will be considered the reference visit for all study visits during Part 2 (Efficacy). Regardless of the occurrence of any unscheduled visits, scheduled visits should be performed within the specified timeframe in relation to Visit 401.

Patients must be seen for all visits on the designated day, or as close to it as possible. Missed or rescheduled visits should not lead to automatic discontinuation. Patients/subjects who prematurely discontinue the study for any reason should be scheduled for a visit as soon as possible, at which time all of the assessments listed for the final visit will be performed. At this final visit, all dispensed investigational product should be reconciled and the adverse event and concomitant medications reconciled on the CRF.

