After Visit 406 (12 weeks), patients using the adult formulation will be seen at 12 week intervals. The liquid formulation of study drug (LCZ696/matching placebo or enalapril/matching placebo) and LCZ696 granules have a limited shelf life. Therefore, Visits 407, 408, 410, 411, 413, 414 are visits intended primarily to permit dispensation of study drug for patients who are using blinded liquid enalapril/matching placebo and/or LCZ696/matching placebo granules. Given the burden of traveling to study visits for patients and families, the parent/caregiver can come to the site for dispensation of study drug. If the parent/caregiver comes to the visit without the patient, a telephone call to the patient (≥ 6 years old) can be used in conjunction with the parent/caregiver visit for the visit assessments (all can be performed verbally). Delivery of study drug to the patient can also be used where possible and allowed per local regulations. At these visits (407, 408, 410, 411, 413, and 414), the following assessments are performed: concomitant medications, AE/SAEs, dosage administration record, study medication compliance, endpoint collection (for additional details refer to Table 6-2). Urine pregnancy testing will be done for females of childbearing potential (for additional details see Table 6-2). IRT will be contacted if study medications are dispensed.

Visits 407, 408, 410, 411, 413, 414 are telephone visits for patients using the adult formulation of study drug. The assessments listed for these visits (Table 6-2) can be performed by telephone.

Patients who prematurely discontinue the investigational treatment will remain in the study and should undergo all the assessments illustrated in Table 6-2. If a patient/parent(s)/legal guardian(s) withdraws from participation in the study, refuses to return for study assessments or is unable to do so, every effort should be made to contact them or a knowledgeable informant by telephone and/or other measures to determine the patient's survival status 52 weeks from randomization (Visit 499).

Patients will be contacted for safety evaluations during the 30 days following the last administration of study treatment.

Table 6-1 Part 1 Assessment Schedule

Epoch	Scree ning			Period 1 st Dose Pk	(				Period 2 ond Dose P	K		Pre- Randomizat ion
Visit	1	101	102 (telephone visit)	103 to 120*	UNS PK/PD	199**	201	202 (telephone visit)	203 to 220*	UNS PK/PD	299**	301** (Part 2 Screening)
Week	•	*	•				•	•				up to -3

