Dosage Administration Record 		Х		Х	Х	х	Х	Х	Х	х	Х	Х	Х	Х	х	Х	Х	(x)	(x)	Х
Study Medication Compliance 		S	S	S	S	S	S	S	S	S	S	S	S	S	S	S	S	(S)	(S)	S
Contact IRT	х	х		Х	Х	х	Х	х	х	х	х	х	Х	Х	х	Х	х	х	Х	Х
Dispense Double-Blind Study Medications		х		Х	Х	х	Х	х	х	х	х	х	Х	Х	х	Х	х		(x)	
Screening Disposition (Parts 1 and 2)	х																			
Endpoints		Х		Х	Х	Х	Х	Х	Х	Х	Х	Х	Х	Х	Х	Х	Х	х	Х	Х
Efficacy Study Treatment Disposition (Part 2)																				х
End of Study Treatment Discontinuation (Part 2)																		х		

UNS = Unscheduled visit

S = assessment to be recorded on source documentation only

TD = Study treatment discontinuation and patient continues study visits;

PSD = Premature subject/patient discontinuation

(x) / (S) = optional assessment

Visit 404 Optional = Investigators have the option to schedule a patient for an additional visit (Visit 404) for up titration.

\*\* A patient may be screened and randomized the same day for Part 2. Visits 299 and 301 (for patient in second dose PK) and Visits 199 and 301 (for patient only going to take first dose PK) may occur on the same day if patient is participating in Part 2. Any assessments should not be repeated if visits occur on the same day.

										Do	uble-bl	ind								
Epoch	Pre- Randomiza -tion																			
Visit	301** (Part 2 Screening)	401	401JPN J	402	403	404 Optional	405	406	407 †	408 †	409	410 †	411 †	412	413 †	414 †	415	UNS/ TD	UNS	416/ 499(PSD)
Week	up to -3	0	1	2	4	6	8	12	16	20	24	28	32	36	40	44	48			52

Confidential

†Visits 407, 408, 410, 411, 413, 414 are telephone visits. Patients who are dispensed LCZ696 liquid formulation/matching placebo, liquid enalapril/matching placebo and LCZ696/matching placebo granules will come to the site for dispensation of study drug. If the parent/caregiver comes to the site without the patient, a telephone call to the patient (≥ 6 years old) can be used in conjunction with the parent/caregiver visit for the visit assessments. IRT will be contacted only if study drug is dispensed.

This must be performed within 1 month of Visit 301 (Part 2). Patients who have participated in Part 1 (PK) and remain in study for Part 2 (efficacy) need a repeat assessment of LVEF or fractional shortening to determine eligibility for Part 2 if the assessment is greater than 1 month prior to Visit 301 (see Section 4.1, Inclusion criteria).

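### Section 3.1 removes patients with angioedema from the study, while Sections 5.5.5, 5.6.2 and 6 stop only study drug and keep follow-up; the possible data loss is small

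*Protocol*

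**What the plan says.** The text on the Part 2 randomized treatment epoch in protocol Section 3.1 states: "Patients who experience angioedema as determined by the Investigator at any time during the double-blind epoch must be discontinued from the study".

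Section 5.6.2 lists circumstances that require permanent discontinuation of study drug. One of them is "Suspected occurrence of angioedema; a patient with any signs or symptoms of clinically significant angioedema". For a permanent stop without withdrawal of consent, the section says "the patient should NOT be considered withdrawn from the study".

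Three other places give the same follow-up rule for any patient who stops drug:

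- Section 5.5.5, on dose adjustments: "then the patient should continue to attend the study visits and be followed until the completion of the study".
- Section 5.5.5, on restarting after interruption: "patients who discontinue study drug should continue to be followed at all study visits as defined in the protocol".
- Section 6: patients who stop treatment early "will remain in the study and should undergo all the assessments illustrated in Table 6-2".

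The legend to Table 6-2 separates two dispositions. One is "TD = Study treatment discontinuation and patient continues study visits"; the other, PSD, is premature discontinuation of the patient.

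Appendix 15, Section 27.2, states that data collected after treatment discontinuation belong in the primary analysis. The only exception is for discontinuations caused by the urgent safety measure (USM).

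**The concern.** Section 3.1 ends participation in the study; every other section ends only treatment. Table 6-2 attaches different data collection to the two outcomes, so this is more than a matter of style. Section 3.1 is also worded as an obligation, whereas Section 5.6.2 is worded as a recommendation, so a site could reasonably treat Section 3.1 as binding and code the patient PSD.

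Visit-based follow-up would then end. Later worsening heart failure, transplant listing, mechanical support, and Week 52 NYHA/Ross, PGIS and PedsQL results could be missed. Section 3.8 names angioedema as a possible risk of LCZ696, so such exits could be related to treatment. The direction of any bias is unknown.

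**Working it through.** **1. The instructions side by side**

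| Place | Trigger | What stops | Follow-up |
|---|---|---|---|
| 3.1 | Angioedema judged present by the investigator | Study participation | Ends |
| 5.6.2 | Suspected angioedema | Study drug, permanently | Patient not withdrawn |
| 5.5.5 | Any temporary or permanent drug stop | Study drug | Visits continue to the end |
| 6 | Any early stop of treatment | Study drug | All Table 6-2 assessments |

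The trigger in 5.6.2 is the wider one. Every patient caught by 3.1 is therefore also caught by 5.6.2, and the two cannot be reconciled as covering different patients.

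**2. Reproducing the plan's figure**

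Inputs are the Table 9-2 percentages for Categories 1 to 5 (LCZ696 9, 15, 8.1, 10.0, 57.9; enalapril 13, 19, 12.2, 11.3, 44.5) and two-sided alpha 0.05 (Section 9.4.2).

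The mid-rank position of each category in the enalapril arm is the share below it plus half its own share: 0.065, 0.225, 0.381, 0.4985, 0.7775. The Mann-Whitney probability is the LCZ696-weighted sum:

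0.00585 + 0.03375 + 0.03086 + 0.04985 + 0.45017 = 0.5705

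Odds = (1 − 0.5705)/0.5705 = 0.753, as stated in Section 9.7.

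The null standard error is √[(1 − Σp³)/(6n)], where p are the pooled proportions and Σp³ = 0.1427. At n = 177 per arm it is 0.0284, and power is Φ(0.0705/0.0284 − 1.96) = 69.9% (plan: about 70%). At n = 180 it is 0.0282, and power is 70.6%.

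**3. Patients affected**

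The documents give no angioedema rate, so 0.2% to 3% is an assumption. 360 × 0.002 = 0.72 and 360 × 0.03 = 10.8 patients, both arms together. For the 375 patients in the Amendment 7 rationale, the range is 0.75 to 11.25.

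**4. Category 1 or 2 events after exit**

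Table 9-2 gives 9 + 15 = 24% (LCZ696) and 13 + 19 = 32% (enalapril) at 12 months. Exponential hazards are −ln(0.76) = 0.274 and −ln(0.68) = 0.386 per year. For a patient who is event-free at exit, the probability of an event in the remaining fraction t of the year is 1 − exp(−hazard × t).

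| Exit | LCZ696 | Enalapril | Mean | Events (0.72 to 10.8 patients) | Events after removing the first 30 days |
|---|---|---|---|---|---|
| Month 3 | 18.6% | 25.1% | 21.9% | 0.16 to 2.36 | 0.14 to 2.07 |
| Month 6 | 12.8% | 17.5% | 15.2% | 0.11 to 1.64 | 0.09 to 1.35 |
| Month 9 | 6.6% | 9.2% | 7.9% | 0.06 to 0.85 | 0.04 to 0.57 |

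The last column supposes that serious adverse event reporting, which runs to 30 days after the final visit (Section 7.2.2), catches every event in that time (mean probability 2.7%). The decimals only trace the arithmetic. The usable answer is roughly 0 to 2 events.

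**5. One unseen event**

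Take one LCZ696 patient whose true outcome is Category 2 but who is ranked higher:

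- Category 3: (0.381 − 0.225)/180 = 0.0009, or 0.03 SE
- Category 4: (0.4985 − 0.225)/180 = 0.0015, or 0.05 SE
- Category 5: (0.7775 − 0.225)/180 = 0.0031, or 0.11 SE

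**6. Power**

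If affected patients contributed nothing, n falls from 180 to 179.64 (0.2%) or 174.6 (3%) per arm, and power falls from 70.6% to 70.5% or 69.3%.

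As an extreme bound, suppose the lost patients were all on LCZ696 and all placed in Category 1. Power would be 67.0% for one patient, 63.3% for two and 55.5% for four. This is unlikely, because an exit assessment and Week 52 survival status are still sought.

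**The case against.** The strongest reply is that this is one loose sentence in a design overview. The paragraph concerns tolerability and itself refers to Section 5.5.5 for guidance, and the operative sections agree with one another. The protocol is loose in the same way about pregnancy: Section 6.5.4 calls for exclusion, while Sections 5.5.5 and 6.5.7 keep the patient in the study. Loose wording is indeed the likely cause, but a wrongly worded rule still needs correcting.

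The second reply is that several safeguards limit the loss:

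- Section 6 gives leavers an exit visit "at which time all of the assessments listed for the final visit will be performed". This records status only at exit.
- Section 6 seeks survival at Week 52 for those who withdraw, refuse or cannot return. This covers survival only, and does not clearly cover a patient removed on protocol instruction.
- Section 9.4.3 asks for every effort to obtain Week 52 information on all patients, then applies a worst-category rule and LOCF. The request helps. The rule works only on information that can be obtained, so it cannot place an event that nobody learns of.
- Worsening heart failure without hospitalization counts in Category 2 but may not be a serious adverse event.

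Three further points stand. Section 5.6.2 sets only a minimum data set after a treatment stop, so even a correctly coded patient might give no Week 52 functional data. The angioedema rate is assumed. Rewording Section 3.1 comes too late to change conduct, because all study drug had to stop by 31 October 2021 (Appendix 15). These points limit the size and the remedy but do not remove the contradiction.

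**Conclusion.** The concern holds, as a minor internal inconsistency. Section 3.1 conflicts with Sections 5.5.5, 5.6.2 and 6 and with the Table 6-2 dispositions, and no supplied text reconciles them. The main SAP, the endpoint committee manual and the angioedema manual were not among the documents reviewed and might do so.

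The likely effect on the primary result is small. It rests on the assumed 0.2% to 3% rate, on Table 9-2 event rates with constant hazards, and on angioedema patients having the same event risk as others. The exclusion of patients with a history of angioedema (Section 4.2) and the 36-hour ACE inhibitor washout (Section 3.1) should keep numbers low. Because deaths are sought separately, the events most at risk of being missed are in Category 2. The documents do not show that any patient was affected. The decision to stop study drug after angioedema is not questioned.

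**What to change.** Before database lock:

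1. List patients with angioedema and check whether any was coded PSD. Cases should be easy to find, because they have dedicated case report forms and external adjudication (Sections 6.5.8 and 8.4).
2. For any such patient, retrieve Week 52 endpoint status where consent allows.
3. Report the count by arm.

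For consistency, reword Section 3.1 to say that these patients must permanently discontinue study drug and continue to be followed to Week 52 unless consent is withdrawn.

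The cost is one query of the disposition records, any retrieval it prompts, and one sentence. No new visits or patients are needed, and the sample size and planned power do not change. The query is the useful part at this stage.
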